6.2.1.1.1. Main Analysis

- Estimand strategy: Hypothetical.
- Analysis set: ACWY-naïve participants: Post-Vaccination 1 evaluable populations for Group 1 and Group 2.
- Analysis methodology: 95% CI for the difference in the percentage of seroresponders (defined as participants achieving a 4-fold rise from baseline for each MenACWY test strain) calculated by the Miettinen and Nurminen procedure.
- Intercurrent events and missing data: Missing serology results will not be imputed. Participants will be summarized according to the vaccine group to which they were randomized.
- The 95% CIs for the difference in the percentage of seroresponders, defined as participants achieving a 4-fold rise from baseline for each MenACWY test strain, 1 month after Vaccination 1 in Group 1 compared to 1 month after Vaccination 1 in Group 2 will be calculated using the Miettinen and Nurminen method. The lower limit of the CI will be used in the hypothesis test for noninferiority as detailed in [Section 5.1](#). Exact 2-sided 95% CIs for the percentages of seroresponders will be provided using the Clopper-Pearson method.

6.2.1.1.2. Sensitivity/Supplementary Analysis

The main analysis will also be performed on the mITT population.

6.2.1.2. hSBA Titer for Each of the MenACWY Test Strains for ACWY-Experienced Participants

6.2.1.2.1. Main Analysis

- Estimand strategy: Hypothetical.
- Analysis set: ACWY-experienced participants: Post-Vaccination 1 evaluable populations for Group 3 and Group 4.
- Analysis methodology: 95% CI for difference in percentage of seroresponders calculated by the Miettinen and Nurminen procedure.
- Intercurrent events and missing data: Missing serology results will not be imputed. Participants will be summarized according to the vaccine group to which they were randomized.

- The 95% CIs for the difference in the percentage of seroresponders, defined as participants achieving a 4-fold rise from baseline for each MenACWY test strain, 1 month after Vaccination 1 in Group 3 compared to 1 month after Vaccination 1 in Group 4 will be calculated using the Miettinen and Nurminen method. The lower limit of the CI will be used in the hypothesis test for noninferiority as detailed in [Section 5.1](#). Exact 2-sided 95% CIs for the percentages of seroresponders will be provided using the Clopper-Pearson method.

6.2.1.2.2. Sensitivity/Supplementary Analysis

The main analysis will also be performed on the mITT population.

6.3. Other Endpoints

6.3.1. Tertiary/Exploratory Endpoints

6.3.1.1. hSBA Titer for Each of the MenACWY Test Strains

6.3.1.1.1. Main Analysis

- Estimand strategy: Hypothetical.
- Analysis set: Post-Vaccination 1 evaluable population for Groups 2 and 4, and post-Vaccination 2 evaluable population for Groups 1 and 3.
- Analysis methodology: In ACWY-naïve and ACWY-experienced participants separately, descriptive summary statistics for MenACWY strains for participants who received at least 1 dose (Groups 2 and 4) of MenACWY-CRM or 2 doses (Groups 1 and 3) of MenABCWY.
- Intercurrent events and missing data: Participants will be summarized according to the vaccine group to which they were randomized. Missing serology data will not be imputed.

For each group (ACWY-naïve and ACWY-experienced participants separately) in the analysis set, the following analysis will be described:

- The percentage of participants achieving an hSBA titer $\geq 1:8$ for each MenACWY test strain, at baseline, 1 month after Vaccination 1 in Groups 2 and 4, and 1 month after Vaccination 2 in Groups 1 and 3.
- hSBA GMTs for each of the MenACWY test strains, at baseline, 1 month after Vaccination 1 in Groups 2 and 4, and 1 month after Vaccination 2 in Groups 1 and 3.

6.3.1.1.2. Sensitivity/Supplementary Analysis

The main analysis will also be performed on the mITT population.

6.3.1.1.3. Main Analysis

- Estimand strategy: Hypothetical.
- Analysis set: mITT population for Groups 2 and 4.
- Analysis methodology: Descriptive summary statistics for MenACWY strains for participants who received at least 1 dose (Groups 2 and 4) of MenACWY-CRM.
- Intercurrent events and missing data: Participants will be summarized according to the vaccine group to which they were randomized. Missing serology data will not be imputed.

For each group (ACWY-naïve and ACWY-experienced participants separately) in the analysis set, the following analysis will be described:

- The percentage of participants achieving an hSBA titer $\geq 1:8$ for each MenACWY test strain, at baseline and 7 months after Vaccination 1 in Groups 2 and 4.
- hSBA GMTs for each of the MenACWY test strains, at baseline and 7 months after Vaccination 1 in Groups 2 and 4.
- The percentage of participants achieving at least a 4-fold rise in hSBA titers for each of the MenACWY test strains, at baseline and 7 months after Vaccination 1 in Groups 2 and 4.

6.3.1.1.4. Main Analysis

- Estimand strategy: Hypothetical.
- Analysis set: Post-Vaccination 1 evaluable population.
- Analysis methodology: Descriptive summary statistics for MenACWY strains for participants who received at least 1 dose of investigational product.
- Intercurrent events and missing data: Participants will be summarized according to the vaccine group to which they were randomized. Missing serology data will not be imputed.

For each group in the analysis set, the following analysis will be described:

- The percentage of participants achieving an hSBA titer $\geq 1:8$ for each MenACWY test strain, at baseline and 1 month after Vaccination 1 in Groups 1 through 4.
- hSBA GMTs for each of the MenACWY test strains, at baseline and 1 month after Vaccination 1 in Groups 1 through 4.

6.3.1.1.5. Sensitivity/Supplementary Analysis

The main analysis will also be performed on the mITT population.

6.3.1.2. Primary MenB Test Strain Evaluations (A22, A56, B24, and B44)

6.3.1.2.1. Main Analysis

- Estimand strategy: Hypothetical.
- Analysis set: Post–Vaccination 2 evaluable population.
- Analysis methodology: Descriptive summary statistics and Clopper-Pearson CIs for primary MenB strains for participants who received 2 doses of the investigational product. Summarized by Groups 1 and 3 combined, and Groups 2 and 4 combined, at baseline and 1 month after Vaccination 2.
- Intercurrent events and missing data: Participants will be summarized according to the vaccine group to which they were randomized. Missing serology data will not be imputed.
- The percentage of participants achieving an hSBA titer \geq LLOQ (1:16 for A22 and 1:8 for A56, B24, and B44) for each primary MenB test strain.
- The percentage of participants with hSBA titers \geq 1:4 for each of the 4 primary MenB test strains.
- hSBA GMTs for each of the 4 primary MenB test strains.

6.3.1.2.2. Sensitivity/Supplementary Analysis

The main analysis will also be performed on the mITT population if there is a difference of more than 10% between the evaluable immunogenicity and mITT populations.

6.3.1.3. Secondary MenB Test Strain Evaluation

The evaluation of the secondary MenB test strains induced by 2 doses of MenABCWY will be reported if requested/required.

6.3.1.3.1. Main Analysis

- Estimand strategy: Hypothetical.
- Analysis set: Post–Vaccination 2 evaluable population.
- Analysis methodology: Descriptive summary statistics and Clopper-Pearson CIs for each secondary MenB test strain in Groups 1 and 3 combined, at baseline and 1 month after Vaccination 2.

- Intercurrent events and missing data: Missing serology results will not be imputed. Participants will be summarized according to the vaccine group to which they were randomized. For each group in the analysis set, the following analysis will be described:
- The percentage of participants achieving an hSBA titer \geq LLOQ for each secondary MenB test strain in Groups 1 + 3 combined, at baseline and 1 month after Vaccination 2.
- The percentage of participants with hSBA titers $\geq 1:4$, $\geq 1:8$, $\geq 1:16$, $\geq 1:32$, $\geq 1:64$, and $\geq 1:128$ for each of the secondary MenB test strains in Groups 1 + 3 combined, at baseline and 1 month after Vaccination 2.
- hSBA GMTs for each of the secondary MenB test strains in Groups 1 + 3 combined, at baseline and 1 month after Vaccination 2.

6.3.1.3.2. Sensitivity/Supplementary Analysis

The main analysis will also be performed on the mITT population if there is a difference of more than 10% between the evaluable immunogenicity and mITT populations.

6.3.1.4. Positive Predictive Value Analyses

PPV analyses of secondary strain response for a given primary strain response within the primary strain subfamily will be performed at 1 month after the second vaccination using the post-Vaccination 2 evaluable immunogenicity population.

For a given time point, the PPV between a primary and secondary strain will be defined as follows: for the participants who had titers \geq LLOQ for the primary strain, the percentage of participants who have titers \geq LLOQ for the secondary strain. The calculation will require available assay results for both the primary and secondary strains.

PPV analyses will be reported if the analysis of the secondary MenB test strains induced by 2 doses of MenABCWY is requested/required.

6.3.1.5. Exploratory Analyses for the Relationship Between Pre- and Post-Vaccination 2 hSBA Titers

Additional exploratory analyses may be performed to investigate the relationship between pre- and post-Vaccination 2 hSBA titers for each of the MenACWY test strains in the ACWY-naïve and ACWY-experienced groups. Scatterplots (with Pearson correlation coefficients) of pre-Vaccination 2 hSBA titers versus fold rises from pre-Vaccination 2 to post-Vaccination 2 using the post-Vaccination 2 evaluable immunogenicity population will be provided. Similar analyses may also be done for pre- and post-Vaccination 1 time points.

6.4. Subset Analyses

Subgroup analyses may be performed on the primary and secondary immunogenicity and safety endpoints described in [Section 6.1.1](#), [Section 6.1.2](#), and [Section 6.2](#). No subgroup analysis is planned for rare events (endpoints with less than 1% of participants in any group). Subgroups can include age strata (10 to <18 years; 18 to <26 years), sex, race, and ethnicity.

If a subgroup variable (eg, race) does not have more than 1 group with greater than 5% participants in the group, the corresponding subset analyses may not be reported.

6.5. Baseline and Other Summaries and Analyses

6.5.1. Study Conduct and Participant Disposition

All participants in the ITT population will be included in the disposition summaries. Summaries will be displayed by randomized vaccine group separately, MenABCWY groups (Groups 1, 3, 5, and 7 combined) and Trumenba groups (Groups 2, 4, 6, and 8 combined).

Disposition summaries include:

- N and % of participants included in each study population (ITT, mITT, post-Vaccination 1 evaluable immunogenicity, and post-Vaccination 2 evaluable immunogenicity).
- N and % of participants receiving each vaccination.
- N and % of participants completing the vaccination phase and follow-up phase.
- N and % of participants who withdrew during the vaccination phase (Visits 1-4) and reason for withdrawal.
- N and % of participants who withdrew during the follow-up phase (After Visit 4 to Visit 5) and reason for withdrawal.

For each blood draw, the number and percentage of participants randomized, vaccinated at each visit (Visits 1 and 3), and providing blood samples within the protocol-specified time frame, as well as before and after the specified time frame, will be tabulated by randomized vaccine group, and total population.

Participant data listings for participants who are included and excluded from each of the analysis populations and reason for exclusion may be provided by randomized vaccine group. A listing of protocol deviations may also be provided.

6.5.2. Vaccine Exposure

Study vaccination data, temporary delays and reasons for vaccination delays, and noncompliant vaccine administration and reasons may be listed by vaccine group as administered. Participants not receiving vaccination as randomized, or randomized to the wrong MenACWY stratum, may be listed by randomized vaccine group.

6.5.3. Demographic, Medical History, and Baseline Characteristics

The safety population will be used to generate the demographic and baseline characteristics summaries.

Variables defined in [Section 3.4.1](#) will be reported according to Pfizer standard summary reporting.

The listings of medical history and baseline physical examination may be provided.

6.5.4. E-Diary Completion

E-diary compliance as defined in [Section 3.6](#) will be summarized for each dose (Vaccination 1, Vaccination 2) by vaccine group, MenABCWY groups (Groups 1, 3, 5, and 7 combined) and Trumenba groups (Groups 2, 4, 6, and 8 combined), and total compliance using descriptive statistics. The safety population will be used to generate the summary reports. The denominator for the e-diary compliance rates will be the total number of participants who received the specific vaccination.

6.5.5. Concomitant Medications and Nondrug Treatments

The listings of nonstudy vaccines and concomitant medications captured throughout the study will be provided according to the WHO Drug Dictionary.

6.6. Safety Summaries and Analyses

All safety data will be summarized according to the vaccine received. The safety population will be used for the analysis.

6.6.1. Adverse Events

It should be recognized that most studies are not designed to reliably demonstrate a causal relationship between the use of a pharmaceutical product and an AE or a group of AEs. Except for select events in unique situations, studies do not employ formal adjudication procedures for the purpose of event classification. As such, safety analysis is generally considered an exploratory analysis and its purpose is to generate hypotheses for further investigation. The 3-tier approach facilitates this exploratory analysis.

Analyses and summaries of primary AE endpoints using the 3-tier approach are described in detail in [Section 6.1.2.5](#).

Tier 3 events will be summarized as part of the overall AE summary.

6.6.1.1. Related Events

AEs and SAEs deemed by the investigator to be related to investigational product will be summarized separately. The denominator for the percentages will be the safety population.

The number and percentage of participants reporting at least 1 related (S)AE and the total number of related events may be summarized by SOC and PT. Associated 95% exact CIs will also be displayed.

6.6.1.2. Severe Events

AEs deemed severe by the investigator may be summarized separately. The denominator for the percentages will be the safety population. The number and percentage of participants reporting at least 1 severe AE and the total number of severe AEs will be reported and will be summarized by SOC and PT. Associated 95% exact CIs will also be displayed.

6.6.1.3. Neuroinflammatory and Autoimmune Conditions

A list of PTs to include all of the neuroinflammatory and autoimmune conditions will be provided by the medical monitor prior to database lock. These events can be SAEs or AEs.

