8.10.1.5. Visit 5 (168 to 196 Days After Last Vaccination), Telephone Contact

- This telephone contact should occur approximately 6 months after the last study vaccination; this contact should be attempted for all participants who have received at least 1 study vaccination, unless they have withdrawn consent.
- Contact the parent(s)/legal guardian or the participant by telephone.

- Complete the Study Visit/Telephone Contact AE Checklist to:
 - Inquire about SAEs, NDCMCs, or AEs that resulted in evaluation at a medical facility since the last visit. Please refer to the SRM for additional details.
 - Inquire about neuroinflammatory and autoimmune conditions, such as transverse myelitis, uveitis, optic neuritis, and multiple sclerosis. A checklist will be provided as a guide. Please refer to the SRM for additional details.
- Report any SAEs to the sponsor as defined in [Section 8.3](#).
- Record AEs as described in the AE reporting requirements section ([Section 8.3](#)) and the [SoA](#).
- Record concomitant medications used to treat AEs as described in the Concomitant Therapy [Section 6.5](#).
- Review AEs that were ongoing since the previous visit and record their end dates or confirm that they are still continuing.
- Complete the source documents.
- Complete the CRFs.

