9.2.2. Additional Participants for Safety Analysis (Groups 5-8)

The sample sizes in Groups 5, 6, 7, and 8 are not based on any hypothesis testing but rather are based on having a sufficient number of participants enrolled to sufficiently characterize the safety profile of MenABCWY. Overall, 1750 participants will be randomized to receive MenABCWY and 663 will be randomized to receive Trumenba + MenACWY-CRM.

Table 10 shows the probability to detect at least 1 AE for different true incidence rates given that 1750 participants will receive MenABCWY.

Table 10. Probabilities of Detecting AEs at Specified Incidences

Sample Size	True Incidence of AE	Probability of Detecting at Least 1 AE
1750	0.001%	1.7%
1750	0.01%	16.1%
1750	0.1%	82.6%

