3.5. Safety Endpoints

3.5.1. Adverse Events

A 3-tier approach will be used to summarize AEs. Under this approach, AEs are classified into 1 of 3 tiers. Different analyses will be performed for different tiers (see [Section 6.6.1](#)).

Tier 1 events: These are prespecified events of clinical importance. There is no Tier 1 event identified for MenABCWY at this stage.

Tier 2 events: These are events that are not Tier 1 but are “relatively common.” A MedDRA PT is defined as a Tier 2 event if there are at least 4 participants in at least 1 combined group reporting the event.

Tier 3 events: These are events that are neither Tier 1 nor Tier 2 events.

The relationship between (S)AEs and the investigational products will be characterized as related or not related as determined by investigators and as described in the protocol. The severity of AEs will be characterized as mild, moderate, and severe.

The time period for actively eliciting and collecting (S)AEs, MAEs, and NDCMCs for each participant is outlined in Table 4.

Table 4. Summary of Adverse Event Collection

	Visits 1-4	Visit 5
Approximate Month	0-7	12
Nonserious AEs	ICD through and including Visit 4 (1 month after Vaccination 2)	
SAEs	ICD through and including Visit 4 (1 month after Vaccination 2)	Since Visit 4
MAEs	ICD through and including Visit 4 (1 month after Vaccination 2)	Since Visit 4
NDCMCs	ICD through and including Visit 4 (1 month after Vaccination 2)	Since Visit 4

Abbreviations: ICD = informed consent document; MAE = medically attended adverse event; NDCMC = newly diagnosed chronic medical condition.

An MAE is defined as a nonserious AE that results in an evaluation at a medical facility, and participants who missed days of school or work because of an AE will be captured via the AE checklist (See [Table 3](#)). Neuroinflammatory and autoimmune conditions will also be captured via the AE checklist. An NDCMC is defined as a disease or medical condition not previously identified that is expected to be persistent or otherwise long-lasting in its effects.

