5.2.1.2. Safety Data

All safety endpoints (including reactogenicity data recorded from the e-diary and AE data recorded from the CRF) will be summarized with percentages and 95% exact CIs (Clopper-Pearson method) for each group.

For both Tier 1 and Tier 2 events (AEs by PTs during the vaccination period), the 95% CIs for the difference in percentage of participants reporting the events between MenABCWY and Trumenba combined groups will be calculated using the Miettinen and Nurminen method.

The CIs presented for the safety data will not be used to test hypotheses but will be used to determine which events may need further clinical investigation. No adjustment for multiplicity is needed. There are no Tier 1 events identified for MenABCWY.

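### No pooled between-group estimate with a confidence interval is specified for the solicited neuroinflammatory and autoimmune conditions

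*SAP*

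**What the plan says.** **Collection.** Protocol 5.2 (criterion 6) excludes people with any neuroinflammatory or autoimmune condition, and Protocol 8.2 asks for particular care in noting them at baseline. The checklist in the Schedule of Activities covers them at Visits 2, 3, 4 and 5. The final telephone contact, about 6 months after the last dose, includes the instruction "Inquire about neuroinflammatory and autoimmune conditions, such as transverse myelitis, uveitis, optic neuritis, and multiple sclerosis" (Protocol 8.10.1.5).

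**Analysis.** SAP 6.6.1.3 reads "A list of PTs to include all of the neuroinflammatory and autoimmune conditions will be provided by the medical monitor prior to database lock" and adds only that the events may be serious or not. The neighbouring sections on related events, severe events, withdrawals and deaths (6.6.1.1, 6.6.1.2, 6.6.1.4, 6.6.1.5) each name an output.

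**Tier rule.** SAP 3.5.1 says of Tier 1: "These are prespecified events of clinical importance. There is no Tier 1 event identified for MenABCWY at this stage". For Tier 2: "A MedDRA PT is defined as a Tier 2 event if there are at least 4 participants in at least 1 combined group". The Miettinen and Nurminen interval for the group difference has this scope in SAP 5.2.1.2: "For both Tier 1 and Tier 2 events (AEs by PTs during the vaccination period". SAP 6.1.2.5 repeats that limit; Protocol 9.4.2 gives the rule without a period.

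**Other outputs.** SAP 6.1.2.5 plans counts, percentages and Clopper-Pearson intervals by group for all AEs. It also says that the percentage difference for the events over the analysis intervals will be shown. SAP Table 5 and 6.1.2.4 count SAEs, MAEs and NDCMCs by group through Visit 5; detail by system organ class and preferred term is optional.

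**The concern.** The conditions are prespecified, actively sought and screened out at entry, so they appear to fit the SAP's own description of Tier 1. Without that status they fall under a rule that works one preferred term at a time. Uncommon conditions of this kind tend to scatter over several terms, so each term may stay below 4 even when the set as a whole does not. Onsets first reported at Visit 5 lie outside the period to which the SAP ties the interval.

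SAP 5.2.1.2 uses these safety intervals to decide which events need further clinical investigation. For this category that screen is not assured. A term list with no stated use also leaves the grouping and time window to be chosen later.

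**Working it through.** **Inputs from the documents**
- Group sizes (Protocol 9.2.2): "Overall, 1750 participants will be randomized to receive MenABCWY and 663 will be randomized to receive Trumenba + MenACWY-CRM". From Protocol Table 1: 450 + 675 + 500 + 125 = 1750 and 225 + 338 + 50 + 50 = 663, about 2.6 to 1.
- Trigger (SAP 3.5.1): at least 4 participants with the same term in at least one combined group.

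**Inputs that are assumptions**
- The incidence of the category. The nearest figure is the Phase 2 rate for all NDCMCs in the vaccination phase, 0.4% with MenABCWY and 0.8% with the comparators (Protocol 2.2.2.3). That is a broader class, so 0.4% is probably high here. Range used: 0.1%, 0.2%, 0.4%.
- The spread over terms: 10 equally frequent terms, counts treated as independent, the same incidence in both groups. Results for 5 and 20 terms are also shown.

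**Step 1. The plan's own figures.** Protocol Table 10 gives the chance of at least one event in 1750 as 1 − (1 − p)^1750. At p = 0.001%, 0.01% and 0.1% this is 1.73%, 16.06% and 82.64%, matching the stated 1.7%, 16.1% and 82.6%. One case is a much lower bar than four of one term.

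**Step 2. One term reaching 4.** For a group of size n, P(X ≥ 4) = 1 − Σ C(n,x) p^x (1 − p)^(n−x), summed over x = 0 to 3. With P1 for n = 1750 and P2 for n = 663, the chance for either group is 1 − (1 − P1)(1 − P2).

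| Incidence of the term | Expected cases (1750 / 663) | P1 | P2 | Either group |
|---|---|---|---|---|
| 0.01% | 0.175 / 0.066 | 0.003% | <0.001% | 0.003% |
| 0.02% | 0.35 / 0.13 | 0.047% | 0.001% | 0.048% |
| 0.04% | 0.70 / 0.27 | 0.57% | 0.02% | 0.59% |
| 0.1% | 1.75 / 0.66 | 10.1% | 0.5% | 10.5% |
| 0.2% | 3.50 / 1.33 | 46.3% | 4.6% | 48.8% |
| 0.4% | 7.00 / 2.65 | 91.9% | 27.5% | 94.1% |

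An even chance of triggering the interval needs about 0.20% for a single term.

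**Step 3. Pooled against split.** With k terms the per-term incidence is the category incidence divided by k, and the chance that any term qualifies is 1 − (1 − q)^k, where q is the last column above. For 0.4% over 10 terms, q = 0.00591 and 1 − (1 − 0.00591)^10 ≈ 0.0575.

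| Category incidence | Pooled, at least 4 | Any of 5 terms | Any of 10 terms | Any of 20 terms |
|---|---|---|---|---|
| 0.1% | 10.5% | 0.24% | 0.03% | <0.01% |
| 0.2% | 48.8% | 2.9% | 0.5% | 0.07% |
| 0.4% | 94.1% | 24.9% | 5.75% | 0.96% |

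**Step 4. What a prespecified event would give.** Tier 1 has no minimum count. Illustrative Miettinen and Nurminen 95% intervals for the pooled difference, MenABCWY minus comparator:
- 3/1750 v 0/663: +0.17 percentage points (−0.41 to 0.50)
- 7/1750 v 0/663: +0.40 (−0.18 to 0.82)
- 7/1750 v 2/663: +0.10 (−0.71 to 0.59)

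**The case against.** The other side has good points.

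- A reader might infer that no between-group comparison at all is planned. The documents do not support that. SAP 6.1.2.5 promises a percentage difference for the events over the analysis intervals. Its scope is unclear and no interval is stated, but read broadly it gives a point difference for every term. It does not pool terms, and the same section confines AEs to the first four intervals, which end at Visit 4.
- A reader might infer that onsets after Visit 4 are lost. They are not: a newly diagnosed chronic autoimmune condition meets the NDCMC definition and is counted by group through Visit 5. It is missing only from the SAP's difference interval, and is not identified as part of this set.
- Nor is this the only solicited topic. The e-diary solicits reactogenicity, and the same checklist covers NDCMCs and medical visits. Being on a checklist does not by itself make an event Tier 1; that is the sponsor's judgement, and the SAP's wording, "There is no Tier 1 event identified for MenABCWY at this stage", leaves it open.
- A reader might suspect that the list could be drawn up with knowledge of allocation. Protocol 6.3.3 keeps the study team blinded, apart from named unblinded roles, so this is not supported either.
- Table shells are prepared separately (SAP 2) and may contain a dedicated output, and the E-DMC sees unblinded safety data. Neither puts a pooled analysis in the plan.
- The intervals would be wide: even a 7 to 0 split includes zero. This stands. Case review remains essential beside the estimate.

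**Conclusion.** The gap is specific. The plan has no pooled between-group estimate with an interval for a category it solicits at four contacts, and the term-level rule is a poor substitute if cases are spread over many terms. At category incidences of 0.1% to 0.4% over 10 terms, the rule yields an interval with probability of about 0.03% to 5.75%. The result depends on two assumptions the documents cannot settle, incidence and number of terms. With 5 terms at 0.4% the chance is 24.9%, and a single term at 0.2% or more would qualify about half the time or better. The pooled chance of reaching 4 (10.5% to 94.1%) shows how much splitting costs; it is not a condition for the fix, since a prespecified event is reported at any count.

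The point does not touch the primary immunogenicity conclusions or the type I error, because the safety intervals test no hypothesis. It is a cheap and worthwhile improvement to the safety analysis.

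**What to change.** In SAP 3.5.1 and 6.6.1.3, fix the preferred-term list before unblinding and define it as one grouped, prespecified Tier 1 event, counting each participant once. For the combined MenABCWY and combined Trumenba groups, report n, % and the Miettinen and Nurminen 95% interval for the difference. Do this for the vaccination phase and for Visits 1 to 5, and add a case listing with term, onset and seriousness. The vaccination-period limit in SAP 5.2.1.2 and 6.1.2.5 needs an exception for this event, and the sentence in 6.1.2.5 on differences over the analysis intervals should say which events it covers.

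The cost is two table rows and one listing; the term list is already planned. The downside is wide intervals, which should be labelled exploratory.
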